9.8 Reporting urgent safety measures

If any urgent safety measures are taken the CI/Sponsor shall immediately and in any event no later than 3 days from the date the measures are taken, give written notice to the MHRA and the relevant REC of the measures taken and the circumstances giving rise to those measures.

9.9 The type and duration of the follow-up of subjects after adverse events.

Treatment will be stopped if a subject develops an unexpected reaction thought to be due to melatonin administration and will be followed up for 24h after the last melatonin dose. Any SUSAR related to the IMP will need to be reported to the Sponsor irrespective of how long after

IMP administration the reaction has occurred. Adverse events and reactions will be recorded for 14d after the last dose of the IMP.

9.10 Development safety update reports

The CI will provide (in addition to the expedited reporting above) DSURs once a year throughout the clinical trial, or on request, to the Ethics Committee, Host NHS Trust and Sponsor.

The report will be submitted within 60 days of the Developmental International Birth Date (DIBD) of the trial each year until the trial is declared ended.

10 STATISTICS AND DATA ANALYSIS

10.1 Sample size calculation

The number of volunteers in this pilot study is a pragmatic number and has been selected based on this being a suitable and sufficient number for a pilot study to enable determination of trial feasibility, including acceptance of the trial design by participants, and drop out rates/retention. In addition we have considered funding issues and previous studies of a similar design [8,34-36]. However, the number chosen and the cross over design will maximise the opportunity for finding any effect. We aim to recruit 32 subjects to cover losses due to drop outs and with the aim of obtaining 25 subjects who complete the protocol. This will allow an initial exploration of potential effects to enable a formal sample size to be calculated for a definitive subsequent trial. We propose that should any subject withdraw or fail to complete both arms of the trial, replacement participants will be sought if this were prior to any treament allocation. Subjects will be randomised in blocks of 8 such that of each 8 participants recruited, four will receive melatonin first and four will receive plaecbo first. The investigators and the subjects will not know the allocation; only pharmacy will know. This scheme will ensure the allocation is evenly spread over the study duration to account for any effects of seasonality.

10.2 Planned recruitment rate

Up to 2 volunteers will be recruited each week once the study has commenced. A CONSORT diagram will be provided (see Appendix 9 for template).

10.3 Statistical analysis plan

Data analysis will be simple descriptive statistics, completer analyses and basic intention to treat assessments of the intervention.

10.3.1 Summary of baseline data

Baseline data will include: Age (numerical). Sex (categorical). Serum cytokine levels (numerical, continuous). Serum melatonin and 6-hydroxymelatonin sulphate levels (numerical, continuous). Verran and Snyder-Halpern sleep scale (numerical, continuous). Epworth sleepiness scale (categorical, ordinal). Data from wristband activity monitor (numerical, continuous). Psychomotor vigilance task (numerical, continuous). Double digit addition test (numerical, continuous). Usual sleep habits (nominal). Composite scale of morningness questionnaires (categorical, ordinal).

10.3.2 Primary outcome analysis

The primary outcome analysis will comprise descriptive summaries describing numbers eligible to take part, those recruited, drop outs (with reasons where possible), non-compliance, number of completers, sex distribution age distribution, type of staff (doctors or nurses), at

baseline and follow-up. The nature of this pilot study means we will not be able to feasibly stratify for sex, age, or type of staff but we will make an assessment of the influence of these possible confounders. Seasonality effects will be minimised by randomising in blocks of 8 subjects.

Summary measures will include mean and standard deviation where data are normally distributed and median and interquartile range where they are not. Paired comparisons of measures after melatonin and placebo treatments; and comparisons of baseline to after nightshift (placebo arm) will be made to explore any possible effects.

Analyses will be on an intention to treat basis, with additional analysis of `completers' (subjects who completed the protocol and received both melatonin and placebo during two separate series of night shifts). These will provide information regarding the biochemical effectiveness of the intervention and the personal effectiveness taking into account aspects of acceptability.

Subjects will be asked to complete a questionnaire about the trial (Appendix 10) which will use a 5 point Likert scale (categorical, nominal). They will also be asked if they will consent to be contacted regarding attending focus groups after the end of the trial (see Appendix 11 for outline discussion schedule) where they will be asked to talk about aspects of the trial. This will be analysed qualitatively after transcription and identification of themes. Focus groups will not be conducted by the trial team, but by an independent qualitative researcher.

10.3.3 Secondary outcome analysis

Summary measures will include mean and standard deviation where data are normally distributed and median and interquartile range where they are not. Paired comparisons of measures after melatonin and placebo treatments; and comparisons of baseline to after nightshift (placebo arm) will be made to explore any possible effects.

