3.1 Primary objective

The primary objective is to undertake a pilot feasibility trial of 6mg slow release melatonin (CircadinTM) before sleep periods compared to placebo in medical and nursing staff working night shifts at Aberdeen Royal Infirmary. The study is a pilot study with no formal sample size calculation.

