3.3 Primary endpoint/outcome

The primary endpoint is successful completion of the trial, defined as recruitment, randomisation and protocol completion of 25 individuals ie both arms of the crossover design. We aim to recruit 32 subjects to account for dropout and non-completion.

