3.5 Secondary endpoints/outcomes

Objectives	Outcome Measures	Timepoint(s) of evaluation of this outcome measure (if applicable)				
Primary Objective	Randomisation of 32 subjects with the aim of 25 completing both arms of the crossover design. This will allow for at least 20% attrition rate which is fairly standard in such studies.					
Secondary Objectives	Determination of drop out, non completion and retention rate	Trial end.				
	Differential gene expression	and end of shifts series on Day 4.				
	Differential gene expression between placebo and active arms.	Blood samples Day 4 after each shift series.				
	Serum IL-6 and TNF α levels.	Blood samples on Day 1, and end of shifts series on Day 4 .				
	Serum IL-6 and TNF α levels after placebo and active arms.	Blood samples Day 4 after each shift series.				
	Serum melatonin and 6- hydroxymelatonin sulphate levels at each time point	Blood samples on Day 1 before shift, and end of each shift for shift series.				
	Verran and Snyder-Halpern sleep scale, Epworth sleepiness scale, data from wristhand activity monitor	VSH before each shift. ESS before, during and after each shift. Activity monitoring during each sleep period.				
	Psychomotor vigilance task, double digit addition test	PVT and DDAT before and after each shift				
	Usual sleep habits and owl-lark questionnaires.	Before randomisation.				
	Questionnaire about trial.	Trial end.				
	Focus group on trial.	Trial end (requires additional consent)				

*Additional consent will be obtained

Figure 1

Summary of the trial design.

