10.5 Adjusted analysis

The nature of this pilot study means we will not be able to feasibly stratify for sex, age, or type of staff but we will make an assessment of the influence of these possible confounders. Seasonality effects will be minimised by randomising in blocks of 8 subjects. We will not adjust for any of these effects.

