10.8 Procedure(s) to account for missing or spurious data

To maximise compliance and follow up, tasks and questionnaire completion before and after shifts will be undertaken with a researcher. The only task required mid shift is the ESS which takes 30 seconds to complete. We will send a text message or set an alarm for the participant to remind them. Taking the trial drug before going to bed can also be prompted by the researcher after the shift and backed up by a text message.

Missing data will not be inputted as this is a feasibility pilot trial. We will record details of missing data points where possible such as reason, where available. The focus group post trial will enable identification of any tasks etc. which participants did not like.

10.9 Other statistical considerations.

We do not anticipate any deviation from the statistical plan unless the trial is stopped prematurely.

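### The crossover comparison has no period term, so any shift between series stays in its variance, and the result labelled intention to treat is nearly the completer result

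*Protocol*

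**What the plan says.** Sections 10.3.2 and 10.3.3 both give the treatment comparison as "Paired comparisons of measures after melatonin and placebo treatments", made to explore possible effects. Neither mentions period or order.

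Section 10.5 lists sex, age, type of staff and seasonality, and says "We will not adjust for any of these effects". Seasonality is handled only by randomising order in blocks of 8 (sections 7.3, 10.1, 10.3.2, 10.4 and 10.5).

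On who is analysed, section 10.3.2 says "Analyses will be on an intention to treat basis", with a further analysis of completers. Section 10.7 defines an all-randomised population that includes people who did not complete both arms. Section 10.8 says "Missing data will not be inputted as this is a feasibility pilot trial", and section 7.9 ends sampling once a participant withdraws after dosing.

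On numbers, section 3.3 says "We aim to recruit 32 subjects to account for dropout and non-completion", with 25 completers as the target. Section 3.1 says "The study is a pilot study with no formal sample size calculation". Section 10.1 nevertheless intends the data to support a formal sample size for a definitive trial.

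**The concern.** In a two-period crossover, a shift between the first and second series raises one order's melatonin-minus-placebo differences and lowers the other's by the same amount. A simple paired comparison treats that spread as noise. The interval widens, and the SD passed to the next trial is too large. If the two orders are unequal in size, part of the shift also enters the estimate.

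The protocol itself gives reasons to expect a shift. It treats season as a threat in several sections. As Table 1 reads, the addition test is taken 7 times per series, so 14 times in all, and the protocol does not say that this test is free of learning.

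Separately, a participant with one series only has no pair. Section 10.3.2 expects the intention-to-treat and completer analyses to give different information, on biochemical effectiveness and on personal effectiveness that reflects acceptability. For paired outcomes they can hardly differ.

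**Working it through.** **The protocol's own figure.** 25 completers at 20% attrition need 25/0.80 = 31.25, rounded up to 32. This matches the planned number. If exactly 25 complete, 7/32 = 21.9% are lost, in line with the statement "This will allow for at least 20% attrition rate which is fairly standard in such studies".

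**Inputs from the protocol.** 32 randomised, 16 to each order (blocks of 8, section 7.3); 25 completers (section 3.3); no imputation (section 10.8).

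**Assumptions, not in the protocol.** The period effect p (second series minus first) is 0.25, 0.5 or 1.0, in units of the SD of the within-person difference within an order. Tests are two-sided at 5%. The true treatment effect for the power figures is 0.6 SD.

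**Formulas.** Let n1 be the number taking melatonin first, n2 the number taking placebo first, and N = n1 + n2. The treatment effect is τ.

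- Expected difference: τ − p (melatonin first) or τ + p (placebo first).
- Mean of the simple paired comparison: τ + p(n2 − n1)/N.
- Variance factor of the paired difference: 1 + p² × 4·n1·n2/[N(N − 1)].
- Standard error with period in the model: 0.5 × √(1/n1 + 1/n2), on N − 2 degrees of freedom, with no bias at any split.

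**Precision at 13/12.** 4 × 13 × 12/(25 × 24) = 1.04, so the variance factor is 1 + 1.04p². With period in the model the 95% half-width is 2.069 × 0.2002 = 0.414 SD for every p.

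| p (SD) | Variance factor | Half-width, simple paired (SD) | Relative to 0.414 | Size of bias (SD) |
|---|---|---|---|---|
| 0 | 1.00 | 0.413 | under 1% narrower | 0 |
| 0.25 | 1.07 | 0.426 | 3% wider | 0.01 |
| 0.5 | 1.26 | 0.463 | 12% wider | 0.02 |
| 1.0 | 2.04 | 0.590 | 42% wider | 0.04 |

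In simulation (40,000 runs per scenario), power at a 0.6 SD effect is 0.82 with period in the model. The simple paired test has 0.72 (p = 0.5) or 0.46 (p = 1.0). Its type I error at 13/12 is below nominal: 0.030 and 0.007.

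**Bias if losses are unequal.** If all seven losses fall in one order, the split is 16/9 and the bias is p × 7/25 = 0.28p. That is 0.14 SD at p = 0.5, with type I error 0.068 (0.083 at p = 1.0). If losses are random, this split has probability 2 × C(16,7)/C(32,7) = 2 × 11,440/3,365,856, about 0.7%. The 13/12 split has probability 0.61, and a difference of 5 or more between orders has probability 0.08.

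**Who enters the comparison.** Only participants with data in both series form a pair: about 25 of 32 at planned attrition. If all seven others have a first-series outcome, a mixed model that keeps them lowers the standard error by 4.6%, 3.4%, 2.1% or 0.7%. These are for assumed within-person correlations of 0.3, 0.5, 0.7 and 0.9.

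**The case against.** **Adjustment for period is not ruled out.** A reader might infer from section 10.5 that it is. The effects named there are sex, age, staff type and season; period and practice are not mentioned. The first three are constant within a person and cancel from a paired treatment difference. So period is omitted, not excluded, and a separate analysis plan could add it. This stands. Even so, the comparison the protocol does state has no period term, and season is expressly left unadjusted.

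**Bias is not the main harm.** A reader might infer that it is. Blocking keeps the orders close to equal unless losses depend on order, and at 13/12 the bias is a few hundredths of an SD. This stands. Blocking does not, however, take a between-series shift out of the variance.

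**Practice and season are limited arguments.** Section 7.7 says the vigilance task does not allow learning, so the practice argument rests on the addition test, one of many secondary measures. A seasonal shift may also differ in size or direction with entry date, and a single period term removes only the part common to all participants. Both points stand.

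**The two analysis sets are not strictly the same.** A reader might infer that they are. A participant with data in both series who missed doses can be in the intention-to-treat pairs without having completed the protocol. The sets are nearly identical, no more.

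**These are exploratory outcomes in a feasibility pilot.** "The primary endpoint is successful completion of the trial, defined as recruitment, randomisation and protocol completion of 25 individuals", and that count does not depend on the paired analysis. This lowers the priority but does not remove the point, because section 10.1 uses the estimates for sizing.

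**Conclusion.** The point holds as a should-level change. The stated analysis gives up precision whenever the two series differ systematically. The loss is negligible to modest for period effects up to 0.5 SD and large at 1.0 SD. If the definitive trial is also a crossover sized on this SD, its sample size is inflated by the same variance factors. All of these figures depend on assumed period effects, since the protocol gives none; with no period effect nothing is lost. Material bias would need losses that differ clearly by order.

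The labelling problem does not depend on those assumptions. Without imputation or sampling after withdrawal, the protocol's paired comparison cannot use the all-randomised population it promises. At planned attrition about 22% of those randomised are outside it.

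**What to change.** 1. In sections 10.3.2 and 10.3.3, for continuous outcomes (transformed where needed), specify a linear mixed model. It has fixed treatment and period and random participant, fitted to all randomised participants with any post-dose data.
2. For ordinal outcomes such as the Epworth scale, or clearly non-normal ones, compare within-person period differences between the two orders by a rank test. This still uses only participants with both series, and should say so.
3. Amend section 10.5 so that it cannot be read as excluding the period term.
4. Keep the simple paired comparison if wanted, labelled as restricted to participants with data in both series.

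The cost is wording and one degree of freedom. If there is no period effect, the interval widens by under 1% at 13/12 and by about 4% at 16/9 (half-width 0.431 against 0.413 SD). No new data are needed. Keeping one-series participants gains only about 1-5% in standard error and relies on losses being explained by the observed data. Its main value is that the analysis then comes closer to its label.

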6.1 Inclusion criteria

Any male or female member of staff working nightshifts to a regular pattern and who can commit to both arms of the study ie 2 series of night shifts approximately 4-6 weeks apart, will be eligible.

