7.7 Trial assessments

Immediately before the first shift subjects will have a baseline blood sample taken and will complete the Epworth Sleepiness Scale (ESS) and the VSH sleep scale [34,42,43]. A baseline personal computer based psychomotor vigilance task (PC-PVT) will be undertaken [44,45]. A double digit addition test (DDAT) will also be used to test problem solving performance, where subjects have to repeatedly add two random double-digit numbers together for a period of 5 minutes (example given in Appendix 8). The percentage of correct answers and the time taken to undertake each addition, plus any lapses, defined as a response time of more than 10s, will be recorded. The worksheet for this is created online and a different sheet will be used each time: http://www.math-aids.com/Addition/Addition_Drills.html.

The ESS will be repeated mid-way through the shift. At the end of the shift, subjects will have another blood sample taken and undertake the PC-PVT and the ESS again before going home, where they will take 6mg melatonin (as Circadin) or a matching placebo with a small snack before going to bed. The means and duration of travel home and the time of dosing and bedtime will be recorded. Subjects will wear a wristwatch style activity monitor during the sleep period, which records activity, sleep and restlessness, REM sleep duration, body temperature and heart rate data that can be downloaded for subsequent analysis.

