Subjects will be asked to wear sunglasses on their journey home if it is light. Subjects will be asked not to attempt to sleep during the day before starting the first night shift and to go to bed as soon as possible when they get home after the shift has ended. They will be asked not to nap during the shift. They will also be asked to refrain from consuming acohol whilst study visits are ongoing. The VSH sleep scale and ESS will be completed again at home when they wake. All PC-PVT tests will be undertaken with a researcher present; the mid-shift ESS will be completed by the subject but a text message reminder will be sent to aid compliance. On each of the next 2 subsequent shifts subjects will undertake the same processes. Around 4-6 weeks later when subjects work another series of night shifts, they will go through the same procedure, but take melatonin if they previously took placebo, and vice versa. Consideration has been given the number of tasks and questionnaires at any one time point to minimise burden and inconvenience such that the time requirement will be no more than 15 minutes in total at any time point.

Biochemical assays

Serum melatonin will be measured using liquid chromatography-tandem mass spectrometry, a method which we have developed in-house. The major metabolite of melatonin, 6-hydroxymelatonin, will be measured in serum as the sulphated form in serum using enzyme immunoassay. Biochemical tests will include urea and electrolytes, liver function tests and differential leucocyte counts. Cytokines (IL-1/6 and TNF α) will be measured using high sensitivity immunoassays. Changes in melatonin/6-hydroxymelatonin and cytokines between melatonin and placebo and between shifts will be determined.

Psychomotor vigilance testing and addition testing

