8.5 Preparation and labelling

Flynn Pharma have supplied the Circadin and matching placebo tablets (2mg) as a single bulk supply from a single batch for dispensing by the Clinical Trials Pharmacy. Commercial stocks of Circadin are provided. Both active and placebo drug will have a shelf-life of 3 years. Drug accountability will be delegated to the Clinical Trials Pharmacist, [name].

Table 1	Study Overview	(applies to both shift series))
---------	----------------	--------------------------------	---

Shift	Blood sample	Sleep habits/CSM questionnaire	PVT/DDAT	Trial drug	VSH sleep scale	ESS	Post trial questionnaire	Focus group*
First shift before shift during shift end of shift before sleeping	4 4 4	~	* *	~	~	4 4 4		
Second shift before shift during shift end of shift before sleeping	~		✓ ✓	~	✓	*		
Third shift before shift during shift end of shift before sleeping	~		* *	~	✓	* * *		
Fourth shift before shift	11		V		4	*		
After all visits							1	✓

 \checkmark = Blood sample for gene array \checkmark = Blood sample for melatonin/cytokines \checkmark = Blood sample for pathology CSM = composite scale of morningness PVT/DDAT = psychomotor vigilance task/double digit addition test VSH = Verran and Snyder-Halpern sleep scale ESS = Epworth sleepiness scale * requires additional consent

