9.7 Overdose

Several cases of overdose of Circadin have been reported post-marketing. Somnolence was the most reported adverse event. Most were mild to moderate in severity. Circadin has been administered at similar daily doses to that proposed here in clinical trials over 12 months without significantly changing the nature of the adverse reactions reported.

If a higher dose than intended is taken, which is highly unlikely, given the trial subjects, the maximum dose they would be able take if they took all their allocated tablets would be 9 x 2mg. We have reported previously that even doses of 100mg melatonin resulted in no adverse events other than mild transient drowsiness. Administration of daily doses of up to 300 mg of melatonin without causing clinically significant adverse reactions have been reported in the literature. If overdose occurs, drowsiness is to be expected. Clearance of the active substance is expected within 12h after ingestion. No special treatment is required. Any subject in whom an overdose occurred would therefore simply be monitored carefully for 24h after overdosing and an adverse event recorded.

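### The night-shift comparison is limited to the placebo arm, which leaves unused the equally undosed first shift of the melatonin series: a loss of precision, not a bias

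*Protocol*

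**What the plan says.** Sections 10.3.2 and 10.3.3 carry the same sentence on the night-shift effect: "comparisons of baseline to after nightshift (placebo arm) will be made to explore any possible effects". Neither section distinguishes the first shift from later ones.

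Section 7.7 fixes the order of events. Baseline blood, sleepiness and vigilance measures are taken immediately before the first shift, and sleepiness is repeated mid-shift. Then: "At the end of the shift, subjects will have another blood sample taken and undertake the PC-PVT and the ESS again before going home". The first tablet follows: participants are assessed "before going home, where they will take 6mg melatonin (as Circadin) or a matching placebo with a small snack before going to bed".

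The second series has the same layout. Section 7.7 says that "they will go through the same procedure, but take melatonin if they previously took placebo, and vice versa", and the title of Table 1 says that it "applies to both shift series". Section 6.1 describes "2 series of night shifts approximately 4-6 weeks apart", and section 9.7 states: "Clearance of the active substance is expected within 12h after ingestion".

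Section 3.2 lists the effect of night working as an objective for the transcriptome and for the cytokine profile. The synopsis names baseline, end of shift on Day 1, and Day 4 as the time points for both, without restriction to an arm. The transcriptome paragraph of section 7.7 instead places the second RNA sample before the second shift.

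**The concern.** The arm label of a series says which tablets were taken in it, not whether a given measurement was made on drug. At the end of shift 1 no tablet of that series has been taken in either arm. Limiting the first-shift contrast to the placebo series therefore leaves out measurements that are just as free of study drug as those it keeps. For melatonin-first participants it leaves out their only drug-naive first shift and keeps the one that follows earlier exposure.

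The night-shift effect matters to this trial. Section 3 says that the study will yield important data even if Circadin has no effect. The rule also loses people: section 7.9 retains data collected before withdrawal, yet a melatonin-first participant who leaves after series 1 has a valid undosed first shift that enters no night-shift comparison.

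**Working it through.** **Completers.** Section 3.5 plans 32 randomised for 25 completers, allowing at least 20% attrition. Check: 25 / 0.80 = 31.25, rounded up to 32. The implied allowance is 7 / 32 = 21.9%.

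**Which measurements are drug-free.** From section 7.7, section 3.5 and Table 1:
- Placebo series: shifts 1, 2 and 3 and the point before shift 4.
- Melatonin series: shift 1 only (before, during and end). Everything later follows at least one dose.

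**Carry-over from an earlier melatonin series.** At the shortest stated spacing, 4 weeks × 7 × 24 = 672 h, against clearance expected within 12 h. Residual drug is no reason to exclude the second series.

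**Share left unused.**
- Baseline to end of shift 1: 25 completers × 2 series = 50 pairs, 25 used, so 50% unused.
- All drug-free shifts: placebo 3, melatonin 1, so 1 / 4 = 25% unused.
- All drug-free sleepiness points: placebo 3 × 3 + 1 = 10, melatonin 3, so 3 / 13 = 23% unused.
- All drug-free vigilance and addition-test points: placebo 2 × 3 + 1 = 7, melatonin 2, so 2 / 9 = 22% unused.

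**Precision.** Let the first-shift change have the same variance in both series and correlation r between a person's two changes. Averaging the two multiplies the variance by (1 + r) / 2. The standard error ratio, both series against placebo only, is therefore √((1 + r) / 2), and the effective number of participants is 25 × 2 / (1 + r). The protocol gives no r, so it is shown over a range.

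| r (assumed) | SE ratio | CI narrower by | Effective n (against 25) |
|---|---|---|---|
| 0 | 0.707 | 29% | 50.0 |
| 0.3 | 0.806 | 19% | 38.5 |
| 0.5 | 0.866 | 13% | 33.3 |
| 0.7 | 0.922 | 8% | 29.4 |
| 1 | 1.000 | 0% | 25.0 |

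**Participants dropped.** With 7 non-completers split evenly by sequence (an assumption; blocks of 8 are balanced 4 and 4), 7 / 2 = 3.5, so about 3 or 4 would be melatonin-first. Not all of these need have completed a first shift.

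**Which outcomes gain.**
- Cytokines: the synopsis names end of shift on Day 1, so a drug-free pair exists in both series.
- Transcriptome: on the synopsis timing a second drug-free pair exists. On the section 7.7 timing, before the second shift, the later sample is post-dose in the melatonin series, which then supplies only a baseline and no pair.
- Vigilance, addition test and sleepiness: pairs exist in both series, but section 3.2 lists these measures only for the effect of Circadin.

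**The case against.** The strongest reply is that the placebo-only comparison is valid and the loss is optional efficiency. The trial is a feasibility pilot without a formal sample size calculation, section 10.3 plans simple descriptive statistics, and these comparisons are exploratory. No precision target is missed. All of this stands, and it sets the weight of the point.

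Second, the sentence may be meant only for post-dose samples. Section 2 links the placebo phase to transcriptome changes when sleep is out of phase with melatonin secretion, and the synopsis has no arm restriction. That reading is possible, but sections 10.3.2 and 10.3.3 state the restriction for the comparison as a whole and make no exception for the first shift. If the narrower meaning is intended, the wording should say so.

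Third, model details are usually left to an analysis plan. That is true of the model, but the restriction to one arm is already stated in the protocol.

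Fourth, the 12 h figure comes from the overdose section and concerns drug clearance only. Other differences between series, such as familiarity with the tests or season, remain possible. This is a reason for a period term and not for exclusion.

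A reader might also infer that half of all drug-free data are discarded. The schedule does not support that: half applies to first-shift pairs, and across all drug-free data the share is about a quarter. Nor is half the pairs half the information, because both pairs come from the same person.

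**Conclusion.** The point holds for contrasts within the first shift. The stated rule uses 25 of 50 available drug-free pairs among 25 completers and omits any melatonin-first participant who leaves after series 1. At r between 0.5 and 0.7 the interval would be 8% to 13% narrower with both series. The 29% figure needs r = 0, and the gain vanishes at r = 1. These figures assume equal variance of the change in the two series and complete pairs.

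A reader might infer that the night-shift estimate is biased, or that the placebo-only rule is wrong throughout. The documents support neither. The placebo series gives a valid estimate, and after the first dose, Day 4 included, it is the only drug-free source. Nor does the gain reach every stated night-shift objective: it is firm for cytokines and conditional on sampling time for the transcriptome. For vigilance, addition test and sleepiness it is an exploratory extra.

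**What to change.** Amend the sentence in sections 10.3.2 and 10.3.3 in three respects:

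1. Estimate contrasts from baseline to during or end of shift 1 from both series, with a random participant effect and a period term. Include participants who supply only one series.
2. Keep the placebo-only rule for all time points after the first dose, including Day 4.
3. Reconcile the second RNA sampling time between the synopsis (end of shift on Day 1) and the transcriptome paragraph of section 7.7 (before the second shift), and apply item 1 to the transcriptome only if it is sampled at end of shift 1.

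The same model gives the between-series repeatability of the first-shift change, which is useful for sizing the definitive trial that section 10.1 has in view. Items 1 and 2 cost only wording, since the schedule already collects these measurements. Item 3 is a clarification that the sampling schedule needs in any case.
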